1. Summary. We will conduct a stepped-wedge cluster randomized controlled trial to evaluate outcomes associated with a direct admission intervention at three health systems: Children's Hospital of Pittsburgh (CHP) in Pittsburgh, Pennsylvania, Nationwide Children's Hospital (NCH) in Columbus, Ohio, and Providence Regional Medical Center (PRMC-E) in Everett, Washington. We have partnered with these health systems given their structural diversity, current low direct admission rates, and strong institutional support to implement and evaluate direct admission processes. A total of 70 practices affiliated with these hospitals will be randomized to cross over from ED admission (usual care at these hospitals) to the direct admission intervention at 4 time points, stratified by practice group. Given 3 practice closures and mergers during the first year of the project, an additional 2 practices will be randomized to participate in the second half of the project. Our primary outcome will be timeliness of clinical care provision. Secondary outcomes include family-reported experience of care and two measures of clinical deterioration: unplanned transfer to the ICU and rapid response calls within 6 hours of hospital admission. We will compare outcomes in children and adolescents with five common diagnoses from practices randomized to the direct admission intervention to those admitted from practices not yet eligible for the intervention, adjusting for appropriate covariates.

2. Conceptual Framework. Direct admission to hospital has several prerequisites, including access to timely ambulatory care for children with acute illnesses, and communication between outpatient and inpatient healthcare providers to initiate direct admission referrals. Our research approach reflects these prerequisites and is modified from Donabedian's structure, process, outcome framework to also incorporate patient characteristics and family preferences (Figure 1).⁴⁵ This framework illustrates how systems factors and processes of care may influence where children access ambulatory care for acute illnesses (ED or primary care clinic) and whether admission occurs directly or through the ED. These factors, in turn, influence health outcomes. The System Factors summarized in this model, including clinic and ED factors, were described by parents of hospitalized children as influential to their decisions about when and where they

pcori

seek

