achieve our research objectives, primary and urgent care practices at each hospital will be randomized to cross over from ED admission to the direct admission intervention using a cluster-randomized stepped wedge design (SWD). The direct admission intervention will be sequentially deployed to 4 groups of practices as shown in Figure 2. This crossover will be unidirectional and occur at 4 time points, with the first two blocks being six months in duration, and the second two blocks being nine months in duration given relatively slow enrollment during the COVID-19 pandemic. Additionally, to increase the number of children in the direct admission arm, we will continue to evaluate the direct admission program during a 9-month maintenance block (months 37-45) at NCH and PRMC-E following the current approach to recruitment and enrollment . Because of

Figure 2. a) Original design: Characteristics of stepped wedge cluster randomized controlled trial, where shaded areas indicate direct admission intervention exposure and unshaded areas indicated control conditions

	TIME (0-36 i	month proje	ect period; e	each block re	epresents 6	months)
	0 mo	6 mo	12 mo	18 mo	24 mo	30 mo
Group 1 (18		DA: 19	DA: 19	DA: 19	DA: 19	
practices)		ED: 87	ED: 87	ED: 87	ED: 87	
Group 2 (18	Pre-	DA: 0	DA: 19	DA: 19	DA: 19	Post-
practices)	rollout	ED: 106	ED: 87	ED: 87	ED: 87	rollout
Group 3 (17	period	DA: 0	DA: 0	DA: 19	DA: 19	period
practices		ED: 106	ED: 106	ED: 87	ED: 87	
Group 4 (17		DA: 0	DA: 0	DA: 0	DA: 19	
practices)		ED: 106	ED: 106	ED: 106	ED: 87	
Rollout period						

(DA = direct admission; ED = ED admission; numbers indicate projected sample size)

b) Modified design given reduced hospitalization volumes during the COVID-19 pandemic, with the 18 and 24 month steps extended to 9 months each, and addition of a 9-month maintenance block (months 37-45).

are projections estimated from enrollment to date)							
	0 mo	6 mo	12 mo	18 mo	27 mo	36 mo	45-50
				(9 mo	(9 mo	(9 mo	mo
				step)	step)	step)	
Group 1		DA: 8	DA: 8	DA: 23	DA: 12	DA: 12	
(18		ED: 129	ED: 92	ED: 216	ED: 232	ED: 148	Post-
practices)	Pre-						rollout
Group 2	rollout	DA: 6	DA: 12	DA: 12	DA: 5	DA: 5	period
(18	period	ED: 85	ED: 61	ED: 147	ED: 172	ED: 117	
practices)							
Group 3		DA: 2	DA: 1	DA: 5	DA: 5	DA: 3	
(18 practices		ED: 132	ED: 66	ED: 153	ED: 145	ED: 85	
Group 4		DA: 6	DA: 5	DA: 10	DA: 22	DA: 22	
(18		ED: 91	ED: 56	ED: 148	ED: 182	ED: 148	
practices)							

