TIME (0-50 month project period; each block represents 6 months unless otherwise specified; the 27mo and 36mo blocks are projections estimated from enrollment to date)

-----Rollout period-----Maintenance

pcori

PRINCIPAL INVESTIGATOR: [name]

very minimal program updake at CHP, we will not evaluate program maintenance at CHP. Figure 2b summarizes our anticipated additional recruitment of patients admitted directly and via emergency department admission at NCH and

PRMC-E, with numbers estimated from actual enrollment to date.

We will randomize 70 primary and urgent care practices: 18 at NCH, 34 at CHP, and 18 at PRMC-E (*Please see LOS from PCP practices affiliated with each hospital*). Practices in each group will be randomized using a stratified approach, with 17-18 practices (4-9 practices per hospital) randomized to crossover to the direct admission intervention at each step/crossover point, stratified by hospital and practice group. Given the closure or merger of 3 practices during the first project year, an additional 2 practices will be randomized to either Group 3 or Group 4, beginning during the 18 month block (Block 3).

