We will first determine crude differences in baseline clinical and sociodemographic characteristics, and in our primary and secondary outcomes, between children admitted directly and through EDs, using t-tests and chi-square tests as appropriate. However, because these unadjusted analyses do not adjust for observed predictors related to direct and ED admission, including temporal trends, for our main analyses we will use regression models. Because all patients receive some form of clinical care at the hospital irrespective of form of admission, there is no censoring associated with the measurement of time to clinical care. Therefore, standard regression models may be used. Patient characteristics incorporated in models will include diagnosis, medical complexity,⁴⁹ level of care (observation versus inpatient), as well as age, gender, race/ethnicity and payer. The statistical model for our direct patient-level comparison of direct admission (DA) versus ED admission patients (analysis i) is

$$Y_{ijht} = \beta_0 + \beta_1 D A_{ijht} + \beta_2 x_{ijht} + \beta_{3t} + \beta_{4h} + \theta_{jh} + \varepsilon_{ijht}$$

in which Y_{ijht} is the outcome variable for patient *i* seen by clinic *j* at hospital *h* at time *t*; DA_{ijht} is a binary variable indicating whether the patient was admitted via direct admission ($DA_{ijht} = 1$) or the ER ($DA_{ijht} = 0$), x_{ijht} is a vector of patient-level controls and θ_{jh} is a random effect for clinic within hospital. In addition, the model includes fixed-effects for time-period, β_{3t} , and hospital, β_{4h} , to capture the general unstructured trend across calendar time and hospitalspecific effects, respectively. The key coefficient of interest is β_1 , which captures the association of a patient being admitted directly versus by an ED with the outcome. A crucial feature of this analysis is that the predictor of primary interest, DA, varies within clinic and time-period mitigating almost all forms of clustering. Therefore, although the data are clustered by clinic and time, the primary source of information about the association of DA with the outcome is from contrasts within clinic and time-period. Hence, accounting for time-period and clinic effects is likely to strengthen the statistical significance of our results.

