When estimating the model in (i), for our primary analysis we plan to only use observations from the post-period. This avoids any contamination from outcomes of ED observations when DA was not available. However, to gain some insight into the closeness of the results from this analysis with those that we'd expect to see if it was possible to have patient-level randomization, in a supplemental analysis we will include the pre-intervention ED observations and test if there is a change in the mean ED outcome in the post-intervention period. A result consistent with minimal change over time will support a finding that, in the absence of the intervention, the outcomes for DA patients would have been the same as those observed for ED patients.

The statistical model for analysis (ii) has a similar form:

$$Y_{ijht} = \beta_0 + \beta_1 Post_{jht} + \beta_2 x_{ijht} + \beta_{3t} + \beta_{4h} + \theta_{jh} + \varepsilon_{ijht}$$

differing only in that the direct admission indicator is replaced with $Post_{jht}$, a time-varying practice within hospital indicator of whether the intervention has been rolled-out (1 = intervention transition has occurred by time period t and 0 = direct admission intervention has not occurred by time-period t). The key coefficient of interest is β_1 , which captures the structural shift in the outcome that occurs when a practice receives the direct admission intervention. Because $Post_{jht}$ does not vary within a clinic and time-period, the information in the observations made within a clinic and time-period depends on the size of the effects of clinic and time-period with the statistical significance of inferences about β_1 is likely to be reduced by the clustering of observations in clinics. An additional component of clustering arises because the four groups are aligned with nine practice groups that in turn are embedded in three hospitals. We acknowledge that there may be separate levels of clustering in the data due to hospital and below that due to practice groups.

However, the nine practice groups emanating from the 3 hospitals will be randomly distributed across the four groups of the stepped-wedge design in a manner that balances the four groups with respect to the characteristics of these groups. Because the practice groups and hospitals are cross-classified with the SWD groups, their effects on the statistical precision of the results will be much less than under a purely hierarchical arrangement.

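### Analysis (ii) gives three dissimilar hospitals one common time trend through COVID-19, so its standard error omits some chance error; hospital-by-period effects would remove this at about 1% cost in precision

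*Combined protocol and SAP*

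**What the plan says.** - **Model terms (D.5, Aim 1).** For analysis (i), "the model includes fixed-effects for time-period" and for hospital, "to capture the general unstructured trend across calendar time and hospitalspecific effects, respectively". The only random term "is a random effect for clinic within hospital". Analysis (ii) has the same form, "differing only in that the direct admission indicator is replaced with" the Post indicator. No hospital-by-period term appears, and no sensitivity analysis on one is planned.
- **Other time terms (D.5).** The plan offers one further covariate, the exact date of the observation, to be added if there is concern about trends inside a block. It is optional and is not described as hospital-specific.
- **Randomisation (D.4).** Crossover is stratified by hospital and practice group, with 18 practices at NCH, 34 at CHP and 18 at PRMC-E.
- **Setting (D.1, D.4, D.6).** The hospitals are in Pennsylvania, Ohio and Washington. Two are children's hospitals with large pediatric EDs. The third is a general hospital with a non-pediatric ED and about 650 child admissions a year. Blocks 3 and 4 were lengthened "given relatively slow enrollment during the COVID-19 pandemic". For the added block in months 37–45, "we will not evaluate program maintenance at CHP".

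**The concern.** The overview in D.5 promises to separate the intervention effect from the effect of time. An additive period term does this fully only if every hospital moved by the same amount in each block. That is doubtful for two children's hospitals and a community hospital in three states during a pandemic. The causal model in D.2 expects direct admission to help partly by removing ED waiting, so local ED load is a plausible driver of the outcome. Volumes certainly moved: the Figure 2b totals are 459 in block 1 and 301 in block 2, each six months long.

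If one hospital's ED slows down in some blocks, the additive model cannot assign the slowdown to that hospital and block. Part of it passes into the Post coefficient whenever the patients who have crossed over are not spread across hospitals in the same proportions as those who have not. Equal practice sizes would nearly prevent this; uneven sizes do not. The stake is the standard error and type I error of analysis (ii), the comparison that rests on the randomised crossover and whose expected effect is small.

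**Working it through.** **1. The plan's own figure (D.8).** Pre-period: ESS 267, mean 85, SD 83. Post-period: ESS 444, mean 76.93, SD 84.99.

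SE = √(83²/267 + 84.99²/444) = √(25.80 + 16.27) = 6.49 min. Power = Φ(8.07/6.49 − 1.96) = Φ(−0.72) = 0.237. The stated 0.23 reproduces.

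**2. Expected Post effect.** The plan's figure is 85 − 76.93 = 8.07 min. Figure 2b gives a smaller one: 154 direct admissions among 2,181 admissions after crossover is 7.1%, and 0.071 × (85 − 40) = 3.2 min. This takes all pre-crossover admissions as ED admissions, as D.3 does. Figure 2b lists some direct admissions before crossover, and counting them would lower the 3.2. Range used: about 3–8 min.

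**3. How a shift reaches the Post coefficient.** The estimate is a weighted sum of practice-by-block means with generalised-least-squares weights a. In the additive model the weights sum to zero over each period and over each hospital, but not over each hospital-period cell. If cell shifts are independent with SD τ, then

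added variance = τ² × Σ over cells (sum of a in the cell)²,

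type I error = 2Φ(−1.96 × SE_model / SE_true), with SE_true² = SE_model² + added variance.

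With hospital-by-period fixed effects every cell sum is zero and nothing leaks.

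**4. Inputs.** From the documents: 18/34/18 practices, crossover stratified by hospital, Figure 2b block totals (459, 301, 714, 775, 540), SD 83, ICC 0.05, and CHP removed from block 5. Inferred from the block 4 and 5 projections in Figure 2b: CHP's volume share is (775 − 540)/775 = 30%; direct-admission shares are (44 − 42)/235 = 0.9% at CHP and 42/540 = 7.8% elsewhere. Assumed: τ, the volume split between NCH and PRMC-E, and the spread of practice sizes. The two practices added at CHP were not modelled.

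**5. Analysis (ii), volumes 50/30/20% (NCH/CHP/PRMC-E).** Model SE 5.61 min.

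| τ (min) | True SE | Added error SD | Type I error |
|---|---|---|---|
| 10 | 5.72 | √(5.72² − 5.61²) = 1.12 | 0.055 |
| 20 | 6.05 | √(6.05² − 5.61²) = 2.27 | 0.070 |
| 30 | 6.57 | √(6.57² − 5.61²) = 3.42 | 0.094 |

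With practice-size coefficients of variation of 0.5 to 1.0, τ of 10–20 min gives an added error SD of about 0.7–2.8 min and a type I error of about 5.2–8%. The upper end depends on the simulated practice sizes and is not sharp. On the plan's own layout (four blocks, 1,696 patients, equal practices) the type I error is only 0.050–0.051 at these τ. With ICC 0.01 it is 0.054 and 0.066 at τ = 10 and 20.

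**6. Bias in (ii) over randomisations.** A +20 min shift at CHP in blocks 3–4 gives a mean of −0.03 min (5–95%: −1.15 to +1.08). A trend of +10 min per block at NCH gives +0.02 (−1.98 to +2.02).

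**7. Block 5 without CHP.** A +20 min shift shared by NCH and PRMC-E gives 0.00; at NCH alone it gives +0.02 (−0.66 to +0.76).

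**8. Analysis (i).** With direct-admission shares constant over time (8/1/8%), bias is 0.00 and type I error 0.050. If the shares drift in opposite directions at NCH and PRMC-E, the NCH trend of +10 min per block gives +1.2 min (+1.8 in a stress case), against an assumed difference of 45 min.

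**9. Cost of the alternative.** The additive terms use 1 + 4 + 2 = 7 parameters. Hospital-by-period cells number 3 × 5 − 1 = 14, seven more. The SE rises from 5.61 to 5.65 min here, and by about 0.3–1.1% over the range in step 5. On the plan's own layout it is 6.01 against 6.02, with power 0.268 either way.

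**The case against.** A common period effect with a random cluster effect is a conventional stepped-wedge model. The plan calls (ii) the indirect version of the hypothesis and gives it power of only 0.23. The documents report reduced volumes and slow enrolment, not hospital-specific changes in time to care, so the shift sizes are hypothetical; at their low end the type I error is practically nominal. All of this stands and limits the weight of the point. It does not show that the common-trend assumption holds, and nothing planned would test it. The argument in D.5 that hospitals are cross-classified with the step groups concerns precision only.

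Two stronger readings are tempting, and the documents support neither.

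- **That both models are biased.** In (ii), stratification by hospital makes the expected bias about zero; what remains is chance error in the one allocation actually drawn. In (i), D.5 notes that the information comes mainly from contrasts within clinic and period, where such shifts cancel. Bias there needs direct-admission shares that drift differently by hospital, and it stayed below about 2 min against 45. Low uptake at CHP is a difference in level, not evidence of drift.
- **That leaving CHP out of block 5 distorts the effect.** By then all practices have crossed over and the block has its own period effect, which absorbs a shift shared by the two remaining hospitals. Estimating that effect from two hospitals is not an error.

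One objection also limits the remedy. The documents give no expected rates for ICU transfer or rapid-response calls within 6 hours. If these are rare, some of 14 cells may have no events.

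**Conclusion.** The point holds for analysis (ii), as one about its standard error rather than bias. The model omits a source of chance error that the hospital-stratified design would let it remove. Under the assumed shifts the harm is modest: the added error SD of up to about 2.8 min is close to the lower end of the expected effect, but only about half of a standard error that is already 5.6 min. It nearly vanishes if practices are of similar size. The conclusion rests on assumed shift sizes, hospital volumes and practice-size variation. The case for changing the plan is that the change costs almost nothing and analyses within the strata used for randomisation.

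**What to change.** In analysis (ii), for time to care and the family-experience scores, replace the separate period and hospital terms with one fixed effect per hospital and period: 14 cells, with none for CHP in block 5. Report the same specification as a sensitivity analysis for (i). Keep the additive terms for ICU transfer and rapid-response calls within 6 hours, and state that possible empty cells are the reason.

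Cost: seven more parameters, a standard error about 0.3–1.1% larger, and a change to the SAP wording. No new data are needed. The percentage was computed for time to care; for the experience scores it also assumes a similar ICC and similar response across hospitals and blocks.

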directly received fewer diagnostic tests and incurred significantly lower healthcare costs than children admitted through the ED with no significant differences in rates of ICU transfer or hospital readmission.³⁷ The second found that direct admission incurred healthcare costs 5-31% lower than ED admission.⁵ The third, focused on the relative risk of unplanned transfers to the ICU among direct- and ED-admitted children at a single children's hospital, found no significant differences in rates of ICU transfer between the groups.³⁸ Based on this systematic review, we conclude: (i) studies examining the comparative effectiveness of direct and ED admission are primarily focused on adult populations with heart disease; it is unknown if the results of these studies will translate to other populations; (ii) the vast majority of existing studies are cohort studies at high risk of bias based on application of a validated risk of bias assessment tool; and (iii) studies in children, a PCORI priority population, are under-represented in the existing literature.

Completion of our proposed research has the potential to fill existing evidence gaps. Our proposed study represents the first RCT study to compare the effectiveness of direct and ED admission. Second, our rigorous design will examine admission processes and outcomes across the diversity of settings where children are admitted to hospital: at two children's hospitals and one general hospital without pediatric subspecialty services.²⁵ Third, we propose a focus on children, a PCORI priority population that is under-represented in research. Fourth, our direct admission intervention, developed based on a process of multistakeholder engagement with parents and both inpatient- and outpatient-based healthcare providers, will examine outcomes prioritized by diverse stakeholders.³⁹ Finally, our proposal to augment our RCT with qualitative analyses of barriers and facilitators of project implementation will provide important contextual information about factors that support and hinder effective direct admission processes.

C. Significance

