Finally, the health outcomes shown were prioritized by these same stakeholders.³⁹ Accordingly this conceptual framework reflects a process of intensive stakeholder engagement in the development of our research question and in selecting our primary and secondary outcomes. **From this Conceptual Framework, our Causal Model may be summarized as follows**: We hypothesize that, by eliminating ED wait times, exposure to the often hectic ED environment, and reducing the number of healthcare teams involved in care provision, directly admitted children will have reduced time to clinical care and improved experiences. The relative benefits of direct admission may differ based on medical complexity, with complex patients, often well known to the hospital-based healthcare teams, more likely to receive timely, personalized care. Primary reason for hospitalization may also influence timeliness of care provision, with conditions requiring minimal diagnostic testing prior to treatment initiation (for example UTIs and SSTIs) having the greatest benefit from direct admission.^{29,35}

3. Comparators. This study will involve a comparison of outcomes in children who are admitted from eligible primary care practices where the direct admission intervention is available (including children admitted directly and through EDs) to those admitted from practices not yet eligible for the intervention (hence all ED admissions). Both ED and direct admission are in current clinical use, with national statistics showing that 25% of children with unplanned hospitalizations are admitted via direct admission while 75% are admitted through EDs.⁵ Children who are transferred from another hospital (inter-hospital transfers) will be excluded, given our inability to account for types and duration of healthcare received at the transferring hospital. All hospitals in the US that receive reimbursement from the Centers for Medicare and Medicaid Services are required to document this variable on Universal Billing forms, and the validity of this variable has been demonstrated in two previous studies.^{46,47}

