Data Adequacy & Management. With the exception of our parent-reported outcome, all required data for this project will be extracted from the hospitals' EHRs; all proposed variables exist in EHRs, thereby minimizing data collection burden and missingness as a result of non-response. During the pre-implementation period, all sites will conduct pilot data extraction from EHRs to assess data source adequacy; any deficiencies will be addressed prior to the rollout. Following data extraction at hospital sites, de-identified data will be sent via HIPAA-secure methods to a secure Dartmouth Research Computing Server, where all data analyses will be conducted and subsequently shared with sites. Prior to study rollout, a comprehensive Data Management Plan will be created with feedback from study sites and stakeholders. Although we anticipate very low rates of **missing data** based on our preliminary work, we will monitor for and report missing data and use multiple imputation to protect analyses against the missing-at-random assumption.^{53,54} In all analyses, we will examine the sensitivity of this approach, and consider this in our interpretation and conclusions.

Aim 1. Determine the effect of a pediatric direct admission intervention on timeliness of healthcare provision (our primary outcome), family experience of care, and rates of clinical deterioration compared to hospital admission beginning in the ED.

We hypothesize that our direct admission intervention will be associated with more rapid initiation of clinical care and improved family experience of care with no significant differences in rates of clinical deterioration (as measured by rapid response calls and unexpected transfer to the ICU). We test two variants of this hypothesis: (i) a patient-level version and (ii) a clinic-level version. The patient-level version is direct in that it evaluates the aim and tests the hypothesis as stated. The clinic-level version is indirect in that it tests whether the intervention has an overall effect across all patients, whether or not they were directly admitted.

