The second part of the calculation is to determine the power of a two-group comparison of a continuous outcome in the absence of clustering when the total sample-size is 711. Because there are 10 group-times in the post-period and 6 in the pre-period each with 106 observations, the split in the ESS between the post and the pre period is 444 and 267. The mean and standard deviation of the outcome in the pre-period is given by the above values for ED admissions; the mean is 85 and the standard deviation is 83. To determine the mean and standard deviation of the outcome expected in the post period, we take weighted averages of the DA and ED admission means and standard, using the total theorem of probability to compute marginal effects. The weight of DA to total patients is 19/106 = 0.094. The weighted average marginal mean and weighted average marginal standard deviation of the observations in the post period are 76.93 and 84.99, respectively. Because the sample-sizes are reasonably large, an asymptotic normal approximation is well justified (i.e., the true distribution of the outcome is bimodal will be averaged out). Given the ESS's and these means and standard deviations, a two-sided 0.05-level test has power of 0.23. In order to have 0.80 power, we would need a much larger effect-size. Specifically, the mean for the post-period would need to be approximately 66.5. Due to the small fraction of ED patients, this will only be plausible if there is a spillover effect of the intervention such that the outcome reduced for DA and ED patients, not just for DA patients.

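### The plan carries two comparisons, by intervention availability (randomised) and by route used (not randomised), without stating their roles or how to read them together

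*Combined protocol and SAP*

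**What the plan says.** **By availability.** D.1 compares children "from practices randomized to the direct admission intervention to those admitted from practices not yet eligible for the intervention". D.3 gives the same definition: "This study will involve a comparison of outcomes in children who are admitted from eligible primary care practices where the direct admission intervention is available", whichever route they took, "to those admitted from practices not yet eligible for the intervention (hence all ED admissions". D.4 (Justification for Study Design) randomises each practice's crossover time. Nothing randomises the route of an individual child.

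**By route.** Hypothesis 1 in Section A is worded as direct admission against admission that begins in the ED. D.5, Aim 1 states: "We test two variants of this hypothesis: (i) a patient-level version and (ii) a clinic-level version". It calls (i) the direct test and (ii) the indirect one. Model (i) has an indicator for the route used; model (ii) replaces it with an indicator that the practice has crossed over. On fitting (i), D.5 says "for our primary analysis we plan to only use observations from the post-period". A supplemental fit adds the pre-intervention ED children and tests whether the mean ED outcome changed. The plan takes little change as support for the view that directly admitted children would otherwise have had the ED outcomes. The Aim 2 subgroup and interaction models are built on (i).

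**Claim and power.** Section B (Evidence Gaps) says: "Our proposed study represents the first RCT study to compare the effectiveness of direct and ED admission". D.8 gives power above 0.99 for (i). For (ii) it says that "a two-sided 0.05-level test has power of 0.23".

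No section ranks (i) and (ii) or says how to interpret them jointly. The remark in D.5 about a substantial difference in results concerns only the two practices added later.

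**The concern.** The design earns its randomised status from the crossover times, and only (ii) uses them. In the main fit of (i) every child comes from a practice that already has the intervention, so its coefficient rests on differences between children who took different routes within the same clinic and period.

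D.7 describes how a child comes to be admitted directly: seen first by the primary care provider (about 13%), referred, then judged appropriate with a bed available (80% accepted). It also assumes that children admitted through the ED may be more acutely ill. The covariates for (i) are diagnosis, complexity, level of care, age, gender, race/ethnicity and payer, with no direct measure of acuity. The documents do not say whether greater acuity would lengthen or shorten time to care, so the bias could run either way.

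At stake is what the trial may conclude. Without stated roles, a route association could be read under the RCT description in Section B, and a null (ii) could be read as evidence of no effect.

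**Working it through.** **Inputs (D.8).** ED mean 85 min, SD 83; direct admission mean 40, SD 28. Analysis (i): 190 direct and 870 ED. Analysis (ii): effective sizes 444 post and 267 pre, post-period mean 76.93, SD 84.99, design effect 2.385. Two-sided alpha 0.05.

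**1. Reproduce the plan's power.** Unequal-SD normal test: z = difference / √(SD₁²/n₁ + SD₂²/n₂); power = Φ(z − 1.96) + Φ(−z − 1.96).
- (i): SE = √(28²/190 + 83²/870) = 3.47; z = 45/3.47 = 12.97; power about 1.00. This agrees with the plan.
- (ii): SE = √(84.99²/444 + 83²/267) = 6.49; z = 8.07/6.49 = 1.244; power 0.24. The plan says 0.23.

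**2. The two targets differ in size.** By route the expected difference is 85 − 40 = 45 min. By availability it is diluted by uptake: 19/106 = 0.179, and 0.179 × 45 = 8.07 min. (D.8 prints this ratio as 0.094, but its mean of 76.93 uses 0.179.)

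**3. Probability that (i) is significant and (ii) is not.**
- Planned effect real: at least 0.99 − 0.23 = 0.76 and at most 1 − 0.23 = 0.77.
- Assumption: no intervention effect, and selection alone leaves the full 45-min gap after adjustment. Then 0.99 − 0.05 = 0.94, up to 0.95.
- Assumption: selection of only 10 to 15 min and no effect. Analysis (i) is significant with probability 0.82 to 0.99 if the SD among directly admitted children is 28, or 0.32 to 0.62 if it is 83.
- No effect and no selection: at most about 0.05, the false-positive rate of (i).

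**4. The supplemental check.** Suppose the children diverted to direct admission would have been δ min faster than the remaining ED children in any case. Removing them raises the ED mean by only 0.179 × δ: 1.8 min for δ = 10, 2.7 for δ = 15, 8.1 for δ = 45. Apply the plan's design effect to the ED children: 870/2.385 = 365 post against 267 pre, with SD 83 in both. Then SE = √(83²/365 + 83²/267) = 6.68. Power to detect even the 8.1-min shift is 0.23 (z = 1.21), and it is 0.06 to 0.07 for the two smaller shifts. Spillover to ED care could also offset such a shift. Little observed change therefore does not show that the two groups are exchangeable.

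**5. Revised projections.** This step assumes the original crossover order in Figure 2b. Post-crossover cells then hold 154 direct and 2,027 ED admissions: 154/2,181 = 7.1%. With control cells treated as all ED, as D.3 does, the expected (ii) difference is 0.0706 × 45 = 3.2 min, with power of about 0.08 at design effect 2.385. (On that order, about 30 direct admissions fall in pre-crossover cells, which needs reconciling with D.3.)

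**The case against.** The strongest reply is that the plan is open about having two analyses. Hypothesis 1 is worded by route, so calling (i) the direct test is accurate on that wording. The sentence on post-period data is about how model (i) is fitted, against its supplemental fit, and does not name (i) as the trial's primary analysis. D.5 calls the coefficient in (i) an association and adjusts for several covariates. D.8 prints the low power of (ii) and explains the dilution. A significant 45-min route difference beside a non-significant 8-min availability difference is what dilution predicts, so the two need not conflict.

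All of that stands. It narrows the point to unstated roles and labels. It does not supply a joint interpretation, nor does it limit the RCT statement in Section B.

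Three stronger readings are tempting and are not supported:
- A reader might infer that a significant (i) would be reported as Hypothesis 1 confirmed by a randomised trial. The RCT statement is background, not a reporting rule, and no section says this.
- A reader might infer that the split pattern is no more likely under a real effect than under none. The 0.94 to 0.95 figure needs an assumed 45-min selection gap; with neither effect nor selection the pattern has probability of at most about 0.05.
- A reader might infer that every claim must rest on (ii), or that a non-significant (ii) should count as failure to confirm. If the planned effect were real, such a rule would return a negative verdict about 76% of the time because of low power.

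**Conclusion.** The point holds as one of labelling and interpretation, and it should be fixed. The plan defines its comparison by availability, words its hypothesis by route, and does not reconcile them. Only (ii) is identified by randomisation. Analysis (i), and the Aim 2 models that follow from it, are adjusted observational comparisons. The check on the ED mean is too weak to change that.

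A split result is the expected one: about 0.76 to 0.77 on the plan's own power figures if its effect is real. That a selection gap would give the same pattern rests on an assumed gap of similar size surviving adjustment; the documents give neither its size nor its direction. The conclusion is therefore only that the pattern cannot by itself distinguish effect from selection. Analysis (i) is not shown to be biased, and it answers a legitimate question.

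**What to change.** 1. In D.3 and D.5, state that (ii) is the randomised estimand, the effect of making the intervention available (about 8 min expected on the original inputs), and that (i) is a non-randomised adjusted association by route used (about 45 min expected).
2. Label (i) and the Aim 2 models built on it as observational. Limit the RCT claim in Section B to (ii). Remove the D.5 sentence that treats a stable ED mean as support for exchangeability.
3. Report both estimates side by side with confidence intervals. State in advance that a significant (i) alone is not randomised evidence of benefit, and that a non-significant (ii) at this power is inconclusive and not evidence of no effect.

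These are changes to plan and reporting text; neither model nor its data changes. The cost is a less favourable headline claim.
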